## 5) Status of administration of concomitant drugs

## ① Use of drugs for JIA

Presence/absence of concomitant drug use for JIA, names of drugs, routes, doses, and durations

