## ② Use of other drugs

Presence/absence of concomitant drug use for conditions other than JIA, names of drugs, routes, doses, and durations

If an adverse event occurs: Names of drugs, reasons for use, routes, doses, and durations

- 6) Non-drug concomitant therapy
  - Non-drug concomitant therapy for JIA
- 7) Presence/absence of tuberculosis or serious respiratory diseases
  - Date of confirmation, method of diagnostic imaging, and presence/absence and type of abnormal findings
- 8) Clinical evaluation
  - Patients will be evaluated for the following at the time points described below:
    - ① DAS28 (number of tender joints and number of swollen joints), global assessment by patient (VAS), global health by physician (VAS), erythrocyte sedimentation rate (ESR, 1 hr value), and CRP. (Baseline, and Weeks 4, 8, 16, and 24 weeks of treatment)
    - ② Serum MMP-3 level. (Baseline, and Weeks 4, 8, 16, and 24 weeks of treatment)
    - ③ Anti-CCP antibody (Baseline and 24 weeks of treatment)
    - ④ Height and body weight. (Baseline, and Weeks 4, 8, 16, and 24 weeks of treatment)
- 9) Discontinuation of Humira treatment
  - Reasons for discontinuation of Humira treatment
  - Treatment after discontinuation of Humira treatment
- 10) Adverse events (including abnormal laboratory findings)
  - Presence/absence of adverse events, nature of adverse events, dates of onset, seriousness, causal relationship with Humira treatment, suspected drugs, clinical course of adverse events, measures taken (measures related to Humira treatment and symptomatic treatment), outcomes, and laboratory findings (indicate laboratory values when abnormal laboratory findings are observed).
- 11) Items of investigation of particular interest
  - Occurrence of infections, tuberculosis, malignant tumor, administration site reactions, autoimmune diseases, pancytopenia, demyelinating disease, congestive heart failure, and interstitial pneumonia.

(4) Preparation of written consent form for transition to self-injection and self-injection transition record

It will be confirmed whether written consent for transition to self-injection has been obtained and a self-injection transition record has been prepared.

(5) Presence/absence of malignant tumor during the long-term follow-up period.

Patients will be evaluated for the occurrence of malignancy during the first and second years of treatment.

(6) Product Quality Complaints

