## 2. Definition of terms and abbreviations

The terms and abbreviations used in this statistical analysis plan are defined as follows.

Terms and abbreviations	Definition
Adverse events	An adverse event refers to any unfavorable and unintended sign (including an abnormal laboratory finding), symptom or disease associated with the use of a drug, whether or not considered related to the drug.
Adverse events during the safety analysis period	Adverse events that occurred during the period up to the start date of Humira treatment + 196 days.
Adverse events outside the safety analysis period	Adverse events that occurred prior to the start date of Humira treatment or after the start date of Humira treatment + 196 days.
Adverse reactions	Of adverse events, events for which causal relationship with Humira cannot be ruled out are defined as adverse reactions.
Adverse reactions during the safety analysis period	Of adverse events during safety analysis period, events for which a causal relationship with Humira cannot be ruled out are defined as adverse reactions during safety analysis period.
Adverse reactions outside the safety analysis period	Of adverse events outside safety analysis period, events for which a causal relationship with Humira cannot be ruled out are defined as adverse reactions outside the safety analysis period.
Basic statistics	Basic statistics include sample size, mean value, standard deviation, minimum value, median value, maximum value, first quartile and third quartile.
MedDRA/J	Medical Dictionary for Regulatory Activities/Japanese edition
SOC	MedDRA/J System Organ Class
PT	MedDRA/J Preferred Term
CDAI	Clinical Disease Activity Index
CRP	C-Reactive Protein
DAS	Disease Activity Score
DMARDs	Disease Modifying Antirheumatic Drugs
EULAR	European League Against Rheumatism
ESR	Erythrocyte Sedimentation Rate
JIA	Juvenile idiopathic arthritis
MTX	Methotrexate
NSAIDs	Non-Steroidal Anti-Inflammatory Drugs
SDAI	Simplified Disease Activity Index
VAS	Visual Analog Scale

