## 10. Data derivation and calculation methods

### 10.1. General

Name of data	Derivation and calculation methods
Age	Use the age shown in the CRF.
Number of investigating facilities	Aggregate the data for each facility code (DCF code).
Number of patients surveyed	Number of patients included in the safety analysis set.
Start date of Humira treatment	Of the start dates of treatment provided in “2. Status of Humira treatment”, the earliest date will be the start date of Humira treatment in each patient. (See “External file for provision of analysis”)
End date of Humira treatment	The latest date sorted by the end dates of treatment provided in “2. Status of Humira treatment” will be the end date of Humira treatment in each patient. (See “External file for provision of analysis”) In the case of ongoing patients, the date on which the final dosing was completed, which is provided in the CRF, will be the end date of Humira treatment. However, in patients whose end date of Humira treatment is “ongoing” or where the end date of Humira treatment calculated as above exceeds the start date of Humira treatment + 168 days, the end date of Humira treatment should be the start date of Humira treatment + 168 days.
Days to the date on which the last dosing of Humira was completed	End date of Humira treatment - Start date of Humira treatment + 1
Treatment status (total number of doses, total dose)	
 
• Total number of doses
 
 
(1) Data on “start date of treatment” and “number of doses” in “2. Status of Humira treatment” should be sorted in the order they are written.
 
(2) Dosing intervals should be calculated for each data on treatment status.
 
The intervals should be 14 days if “biweekly” is checked. If not, the intervals should be obtained from “External file for provision of analysis”.
 
(3) The number of doses should be calculated for each data on treatment status.
 
Number of doses = (end date of treatment [after complementation] - start date of treatment [after complementation])/dosing intervals (days)
 
*The end date of treatment in the last record should be the end date of Humira treatment.
 
(4) If the result of (3) is “>0” (greater than 0) and “<1” (smaller than

Name of data	Derivation and calculation methods

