Previous medication (biological product): tocilizumab	“With previous medication (biological product): tocilizumab” should be selected when the drug meets the conditions of “previous medications (biological products)” and the higher order 7 digits of the drug code of the previous medication (biological product) are “6399421”, “unknown/unspecified” should be selected when the history of treatment with previous medications (biological products) is “unknown/unspecified”, and “without previous medication (biological product): tocilizumab” should be selected otherwise.
Previous medication (biological product): etanercept	“With previous medication (biological product): etanercept” should be selected when the drug meets the conditions of “previous medications (biological products)” and the higher order 7 digits of the drug code of the previous medication (biological product) are “3999424”, “unknown/unspecified” should be selected when the history of treatment with previous medications (biological products) is “unknown/unspecified”, and “without previous medication (biological product): etanercept” should be selected otherwise.
Previous medication (biological product): other	“With previous medication (biological product): other” should be selected when the drug meets the conditions of “previous medications (biological products)” and the higher order 7 digits of the drug code of the previous medication (biological product) are other than “6399421” and “3999424” and the drug falls under “Biological products” in “Drug code list_20171012.xlsx”, “unknown/unspecified” should be selected when the history of treatment with previous medications (biological products) is “unknown/unspecified”, and “without previous medication (biological product): other” should be selected otherwise.
Concomitant drugs	Concomitant drugs are defined as drugs listed in “5. Previous medications for juvenile idiopathic arthritis”, “6. Status of

Name of data	Derivation and calculation methods
	administration of concomitant drugs (1) [Concomitant drugs for juvenile idiopathic arthritis]”, “6. Status of administration of concomitant drugs (2) [Other concomitant drugs]” in the CRF and confirmed to have been administered between the start date of Humira treatment and the end date of Humira treatment.

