Status of concomitant drugs	“With concomitant drugs” should be selected when the patient is treated with concomitant drugs, “unknown/unspecified” should be selected when “Status of previous medications for juvenile idiopathic arthritis/concomitant drugs for juvenile idiopathic arthritis/other concomitant drugs” is not specified or indeterminable, and “without concomitant drugs” should be selected otherwise.
Concomitant drug: methotrexate	“With concomitant drug: methotrexate” should be selected when the conditions for “concomitant drugs” are met and the concomitant drug falls under “MTX” in “Drug code list_20171012.xlsx”, “unknown/unspecified” should be selected when the status of concomitant drugs is “unknown/unspecified”, and “without concomitant drug: methotrexate” should be selected otherwise.
Concomitant drug: corticosteroid	“With concomitant drug: corticosteroid” should be selected when the conditions for “concomitant drugs” are met and the concomitant drug falls under “steroid (oral + injection)” in “Drug code list_20171012.xlsx”, “unknown/unspecified” should be selected when the status of concomitant drugs is “unknown/unspecified”, and “without concomitant drug: corticosteroid” should be selected otherwise.
Concomitant drug: NSAIDs	“With concomitant drug: NSAIDs” should be selected when the conditions for “concomitant drugs” are met and the concomitant drug falls under “NSAIDs (oral + injection)” in “Drug code list_20171012.xlsx”, “unknown/unspecified” should be selected when the status of concomitant drugs is “unknown/unspecified”, and “without concomitant drug: NSAIDs” should be selected otherwise.
Concomitant drug: other DMARDs	“With concomitant drug: other DMARDs” should be selected when the drug meets the conditions for “concomitant drugs” and does not fall under “MTX” and falls under “DMARDs” in “Drug code list_20171012.xlsx”, “unknown/unspecified” should be selected when the status of concomitant drugs is “unknown/unspecified”, and “without concomitant drug: other DMARDs” should be selected otherwise.
Concomitant drug: Other drugs	“With concomitant drug: other drugs” should be selected when the drug meets the conditions for “concomitant drugs” and does not fall under “MTX”, “steroid (oral + injection)” or “DMARDs” in “Drug code list_20171012.xlsx”, “unknown/unspecified” should be selected when the status of concomitant drugs is “unknown/unspecified”, and

Name of data	Derivation and calculation methods

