Name of data	Derivation and calculation methods
	
body surface area should be calculated.
 $S = W^{0.425} \times H^{0.725} \times 71.84$ 
S = body surface area (cm^2); W = body weight from the start date of Humira treatment - 28 days to the start date of Humira treatment (kg); H = height from the start date of Humira treatment - 28 days to the start date of Humira treatment (cm)
 
If the dose of methotrexate was changed during the survey period, calculate doses per body surface area for each record and calculate the mean value.

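### Concomitant-drug and MTX-dose factors tested in Tables 2.5.1, 3.1 and 3.5.2 can be set by what happens after the outcome, so reverse causation can produce a significant factor

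*SAP*

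**What the plan says.** **Exposure.** SAP 10.1 takes concomitant drugs from CRF sections 5, 6(1) and 6(2), provided they were "confirmed to have been administered between the start date of Humira treatment and the end date of Humira treatment". For ongoing or longer treatment, "the end date of Humira treatment should be the start date of Humira treatment + 168 days". Corticosteroid status then requires that "the concomitant drug falls under “steroid (oral + injection)” in “Drug code list_20171012.xlsx", and NSAID status that "the concomitant drug falls under “NSAIDs (oral + injection)” in “Drug code list_20171012.xlsx". Topical products do not count.

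**MTX class.** Height and weight come from the 28 days up to Humira start. If the dose changed, the instruction is to "calculate doses per body surface area for each record and calculate the mean value". SAP 11 sets class limits at 4, 7 and 10 mg/m²/week.

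**Outcome.** The safety analysis period covers "Adverse events that occurred during the period up to the start date of Humira treatment + 196 days". The final efficacy assessment in SAP 12 also runs to +196 days.

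**Use.** Tables 2.5.1, 3.1 and 3.5.2 test these variables with Fisher's exact test or the Mann-Whitney U test, at two-sided 5% (SAP 9.14). A factor with p<0.05 in Table 2.5.1 gets its own Table 2.5.5.X.

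**Collection.** Protocol section 8(3) item 5) collects, for JIA drugs, "Presence/absence of concomitant drug use for JIA, names of drugs, routes, doses, and durations" and, for other drugs, "Presence/absence of concomitant drug use for conditions other than JIA, names of drugs, routes, doses, and durations". The latter heading adds drug names and reasons for use if an adverse event occurs. Item 10) of the same section separately records symptomatic treatment with the adverse event.

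**The concern.** A background factor should be fixed before the outcome it is meant to explain. Here the exposure window lies inside the outcome window, and neither the order of drug and event nor the reason for use is consulted. Three routes follow:

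- A patient not on a systemic steroid or NSAID has a reaction, is given one, and is classed as a user. The drug then looks harmful.
- MTX is reduced after a reaction, the record mean falls, and the patient moves to a lower dose class. The high dose then looks safe.
- A drug is added, or a dose raised, for poor response. The drug then looks linked to non-remission in Tables 3.1 and 3.5.2.

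Factors affecting safety and efficacy are a stated purpose in both documents, and SAP 3.1 says results may feed regulatory reporting and the reexamination application. What is at stake is a misleading statement about a factor.

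**Working it through.** **The plan's own figure.** Protocol section 2 gives 100 patients for a 95% chance of seeing a reaction of 3% incidence: 1 − 0.97^100 = 0.952, which reproduces. It supplies n but says nothing about factor tests. The documents give no reaction rate, drug-use rate or frequency of MTX change, so everything below is assumption shown as a range.

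**Steroid or NSAID against reactions (Table 2.5.1).** Take 30 reactors and 70 non-reactors, with no true effect. Let b be use at Humira start, and s the share of those not already on the drug who start it later (s1 in reactors, s0 in non-reactors). Then

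P(classed as user) = b + (1 − b)s.

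For b = 20% and s1 = 0.2 this is 0.20 + 0.80 × 0.2 = 0.36, against 0.20 in non-reactors: odds ratio (0.36/0.64)/(0.20/0.80) = 2.25. Exact enumeration of both binomials gives the chance of Fisher p<0.05:

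| s1 v s0 | b=20% | 40% | 60% | 80% |
|---|---|---|---|---|
| 0 v 0 | 3.2% | 4.2% | 4.2% | 3.2% |
| 0.05 v 0 | 5.8% | 5.1% | 4.5% | 3.2% |
| 0.10 v 0 | 12.1% | 7.6% | 5.6% | 3.3% |
| 0.20 v 0 | 35.5% | 17.9% | 10.0% | 4.4% |
| 0.20 v 0.10 | 10.6% | 7.1% | 5.2% | 3.2% |

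As single tables: 6/30 v 14/70 users gives p = 1.00. If six of the 24 untreated reactors are then given the drug, 12/30 v 14/70 gives p = 0.048.

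**Early stopping.** Stopping Humira closes the drug window, so later treatment is not counted. Suppose half the reactors stop, have no treatment starts counted and have half the background window. With 10% treatment starts and 10% background starts in everyone, s1 = 0.5 × 0.05 + 0.5 × (1 − 0.9 × 0.9) = 0.12 against s0 = 0.10. The rates are then 4.0/4.2/4.0/3.1%: the effect is gone.

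**MTX class.** A cut from 9 to 4.5 mg/m² has a record mean of (9 + 4.5)/2 = 6.75, so the patient moves from the 7-to-<10 class to the 4-to-<7 class. This uses a simple mean; the SAP mentions no weighting. In simulation with 60 and 80 MTX users, 30% with a reaction, and doses of mean 8 and SD 2.5 (assumed), halving the dose in 20% of reactors on MTX gives p<0.05 in 8.0% and 9.7% of runs. Halving in 40% gives 18.9% and 23.1%. The dose at Humira start gives about 5%. In a second simulation (doses uniform from 4 to 14 mg/m²) in which half of the changes are complete stops that leave no lower-dose record, the rates for 60 and 80 users are 5.7% and 5.6% (20% changed), and 8.3% and 9.4% (40% changed).

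**Efficacy (Tables 3.1 and 3.5.2).** Assume 80 patients and 30-70% remission. Excess starts of 10 to 20 points in non-remitters give about 8-29%, 6-15%, 4-9% and 3-5% at b = 20/40/60/80%, against 3-4% with no excess.

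**The case against.** The strongest objection is that the safety route is not established. Symptomatic treatment has its own place in protocol item 10), which SAP 10.1 does not name as a source of concomitant drugs. The line on drugs and reasons for use when an event occurs may mean treatments, or only drugs already in use at the time. A reader might infer that the plan certainly counts treatment of reactions as exposure. The documents do not support that: the CRF is not shown, so the route is likely but not certain. The window definition and the MTX averaging rule do not depend on this point.

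The second is size. Patients have failed conventional therapy (protocol section 3), so baseline use may be high, and there the inflation is slight. The large figures need low use, a 20-point excess and little early stopping. This stands, and it limits the finding.

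The third is consequence. Table 2.5.1 tests 31 factors without adjustment, so at 3-5% each about 0.9 to 1.6 chance positives are expected anyway. A positive leads only to a descriptive breakdown, and Tables 3.1 and 3.5.2 trigger nothing. Previous use of the same drug classes (days −90 to −1) is tested alongside, and onset and drug dates are listed in Tables 4.2 and 4.3.4. These help a careful reader, but they do not correct the test, and previous use does not show use at Humira start.

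A reader might also extend the point to administration method. The documents give no ground for dropping that test: it does not take up drugs given for a reaction, and illustrative runs put it at 5.9-8.4% against 5.3%, which is small.

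**Conclusion.** The point holds as a defect of definition: the tested variables do not control the order of exposure and outcome, and the direction of the resulting bias is predictable. Its size cannot be taken from the documents. Under the stated assumptions (100 patients, 30% with a reaction, no true effect, 10 to 20 points of excess starts in reactors), the false-significance rate is 12-35% at 20% baseline use, 8-18% at 40%, 6-10% at 60% and 3-4% at 80%, against 3-4% with no excess. It is less, or nil, if Humira is often stopped early.

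The factors most exposed are corticosteroid, NSAID and MTX class. It would go too far to conclude that the factor results will be wrong, or that a regulatory decision turns on them, since no decision rule is attached. The change is worth making because it is cheap and the question is a stated purpose of the survey.

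**What to change.** For the tests in Tables 2.5.1, 3.1 and 3.5.2, and for the Table 2.5.5.X trigger:

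- Classify corticosteroid, NSAID, MTX, other-DMARD and overall concomitant use by records in force on the Humira start date: record start on or before that date, and record end on or after it or ongoing.
- Take the MTX mg/m²/week class from the dose in force on that date.
- Keep the whole-period versions as descriptive rows labelled on-treatment, with no test and no trigger.
- Leave the administration method test as it is.

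Using one definition for all the drug factors keeps the safety and efficacy tables consistent, although some of them are little affected.

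The cost is SAP wording and a re-derivation. Doses and durations are already collected, and drug dates are already output in Table 4.3.4. There are three downsides. Drugs started after Humira but before a reaction leave the tested factor, though they stay in the descriptive rows and listings. Records with incomplete dates become unknown and leave the test (SAP 9.2 and 9.3). Confounding by disease severity remains, because sicker patients may be on more drugs at the start; the change removes reverse causation only.

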Data	Layer separation
disorder	
Complication: Cardiovascular disorder	No, yes, unknown/unspecified
Complication: Blood disorder	No, yes, unknown/unspecified
Complication: Respiratory disorder	No, yes, unknown/unspecified
Complication: Other	No, yes, unknown/unspecified
History of allergy	No, yes, unknown/unspecified
Breakdown of history of allergy	Drug, food, other
Previous medications	No, yes, unknown/unspecified
Breakdown of previous medications	Methotrexate, corticosteroid, NSAIDs, other DMARDs
History of treatment with previous medications (biological products)	No, yes, unknown/unspecified
Breakdown of history of treatment with previous medications (biological products)	Tocilizumab, etanercept, other
Concomitant drugs	No, yes, unknown/unspecified
Breakdown of combination drugs	Methotrexate, corticosteroid, NSAIDs, other DMARDs, other drugs
Tuberculin skin test	Tested, not tested, unknown/unspecified
Quantiferon test (including T-SPOT)	Tested, not tested, unknown/unspecified
Chest x-ray	Tested, not tested, unknown/unspecified
Chest CT	Tested, not tested, unknown/unspecified
Immunology test (tuberculin skin test or Quantiferon test or T-SPOT)	No, yes, unknown/unspecified
Image testing (chest x-ray or chest CT)	No, yes, unknown/unspecified
Prophylactic administration (status of prophylactic administration by	No, yes, unknown/unspecified

Data	Layer separation
implementation status of tuberculosis tests)	
HBs antigen test	Implemented (negative, positive, unknown/unspecified, subtotal), not implemented, unknown/unspecified
HBs antibody test	Implemented (negative, positive, unknown/unspecified, subtotal), not implemented, unknown/unspecified
HBc antibody test	Implemented (negative, positive, unknown/unspecified, subtotal), not implemented, unknown/unspecified
Status of Humira treatment (dosage and administration)	20 mg/2 weeks, 40 mg/2 weeks, 20 mg/2 weeks → 40 mg/2 weeks, other
Number of doses	≥1 to <2 doses, ≥2 to <6 doses, ≥6 to <12 doses, ≥12 doses
Days to the date of the last dosing	1 to 28 days, 29 to 84 days, 85 to 168 days, ongoing at day 169
Dose at the start of Humira treatment	20 mg, 40 mg, 80 mg, other, unknown/undescribed
Dosage and administration category	Dose increase group (20 mg → 40 mg), maintained dose group, other, unknown/unspecified
Self-administration	No, yes, unknown/unspecified
Error caused by self-administration	No, yes, unknown/unspecified

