- The denominator of the percentage of switched patients should be patients included in the safety analysis set, and the denominator of the percentage in the breakdown of the reasons for switching should be patients switched to other biological products as defined in “10.1 General”.
- “Onset of an adverse event” should apply only when “Onset of an adverse event” is selected and an adverse event during safety analysis period has occurred.

“Table 1.3 Aggregate results of patient background”

Analysis object: Patients included in the safety analysis set, patients included in the efficacy analysis set

Purpose of analysis: The number and percentage of patients by patient background will be calculated.

For quantitative data, basic statistics will also be calculated.

Patient background should follow “11. Data-layer separation” (sex, pregnancy/breastfeeding, age 1, age 2, age 3, body weight, BMI, inpatient/outpatient status at the start of Humira treatment, reason for use and type of disease, disease duration 1, disease duration 2, race, Steinbrocker Staging System, Steinbrocker Functional Classification, administration method category, past medical history, complications, breakdown of complications, history of allergy, breakdown of history of allergy, previous medications, breakdown of previous medications, history of treatment with previous

medications [biological products], breakdown of history of treatment with previous medications [biological products], concomitant drugs, breakdown of concomitant drugs, of the breakdown of concomitant drugs, dose of methotrexate per body surface area, concomitant drug [methotrexate], breakdown of concomitant drug [methotrexate]).

Notes:

- The denominator of the percentage of patients falling under pregnancy/breastfeeding should be “female” (sex) patients.
- The denominators of percentages in items other than the above should be the upper-rank analysis set.
- The reason for use and type of disease, breakdown of complications, breakdown of history of allergy, breakdown of previous medications, breakdown of history of treatment with of previous medications (biological products), breakdown of concomitant drugs, and breakdown of concomitant drug (methotrexate) may be redundantly aggregated.

“Table 1.4 Implementation status of tuberculosis tests (1) (implementation rate of each test)”

Analysis object: Patients included in the safety analysis set

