Purpose of analysis: Involving adverse reactions during the safety analysis period, the number of patients and the number and percentage of patients who experienced adverse reactions will be calculated in accordance with “11. Data-layer separation” (age 1, age 2, age 3, sex, body weight, BMI, reason for use and type of disease, disease duration 2, complications, complication: liver disorder, complication: renal disorder, complication: cardiovascular disorder, complication: blood disorder, complication: respiratory disorder, complication: other, past medical history, history of allergy, Steinbrocker Staging System, Steinbrocker Functional Classification, administration method category, previous medications, status of previous medication: biological product, status of previous medication: MTX, status of previous medication: corticosteroid, status of previous medication: NSAIDs, status of previous medication: Other DMARDs, concomitant drugs, status of concomitant drug: MTX, status of MTX: details, status of concomitant drug: corticosteroid, status of concomitant drug: NSAIDs, status of concomitant drug: Other DMARDs).

For the incidence rates of adverse reactions, Fisher's exact test should be conducted when the background factor is a nominal scale and Mann-Whitney U test should be conducted when the background factor is an ordinal scale.

Notes: • Reason for use and type of disease may be redundantly aggregated. No test will be conducted for this item.

“Table 2.5.2 Incidence of adverse events in patients switched to other biological products”

Analysis object: Patients included in the safety analysis set

Purpose of analysis: Involving adverse events during the safety analysis period, the number of patients, the number and percentage of patients who experienced adverse events will be calculated on the basis of the number of patients switched to

other biological products and the breakdown of the reasons for switching (remission, subtherapeutic response, onset of adverse events, patient's request, no hospital visit [including hospital transfer], other).

Notes:

- The breakdown of the reasons for switching may be redundantly aggregated.
- “Onset of an adverse event” should apply only when “Onset of an adverse event” is selected and an adverse event during safety analysis period has occurred.

“Table 2.5.3 Incidence of adverse reactions to combination therapy for juvenile idiopathic arthritis”

Analysis object: Patients included in the safety analysis set

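### The concomitant 'other drugs' class does not exclude NSAIDs, so each oral or injected NSAID counts in two rows of SAP Table 1.3

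*SAP*

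**What the plan says.** SAP section 10.1 derives five concomitant-drug classes from a drug code list. The NSAID class is met when "the concomitant drug falls under “NSAIDs (oral + injection)” in “Drug code list_20171012.xlsx". The 'other drugs' class is met by a concomitant drug that "does not fall under “MTX”, “steroid (oral + injection)” or “DMARDs". That exclusion list has three entries, and NSAIDs are not one of them.

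SAP section 11 sets out the breakdown of concomitant drugs as five parallel layers: "Methotrexate, corticosteroid, NSAIDs, other DMARDs, other drugs".

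Table 1.3 (SAP section 13.1) reports this breakdown for the safety analysis set and the efficacy analysis set. Its notes say that the "breakdown of concomitant drugs, and breakdown of concomitant drug (methotrexate) may be redundantly aggregated". Section 9.10 asks for a footnote wherever an item is counted redundantly.

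**The concern.** When four classes are named and a fifth is called 'other', a reader takes the fifth to be the remainder. The SAP builds its comparable classes that way. 'Other DMARDs' removes MTX, and the 'other' class of previous biological products removes both named products by drug code. The concomitant 'other drugs' class alone leaves one of its named siblings in.

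What is at stake is the reading of one row in the patient-background table. SAP section 3.1 says the results feed regulatory reporting and the reexamination application. Someone using Table 1.3 to see how many patients took drugs outside the four named classes would get a figure that also contains every oral or injected NSAID user. The overlap is unlikely to be empty, since section 8 of the protocol lists NSAIDs among the JIA treatments to be recorded.

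**Working it through.** The plan states no figure that depends on this rule, so there is none to reproduce. The check has three parts.

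**1. Apply the section 10.1 rules to one drug of each kind.**

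| Concomitant drug | NSAIDs | Other drugs, as written | Other drugs, NSAIDs also excluded |
|---|---|---|---|
| MTX | no | no | no |
| Steroid (oral or injection) | no | no | no |
| Other DMARD | no | no | no |
| NSAID (oral or injection) | yes | **yes** | **no** |
| Drug in no listed class | no | yes | yes |

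Only the NSAID line changes. The unknown/unspecified branch of the definition does not rescue it, because a patient with an NSAID record already counts as having concomitant drugs.

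**2. Size of the overstatement.** The documents give no usage rates, so both inputs are assumptions: p is the proportion taking an oral or injected NSAID, and q the proportion taking a genuinely other drug (none of the four named classes).

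- Row under the remainder rule: q.
- Row as written: the proportion taking either kind of drug. Under independence this is 1 - (1-p)(1-q).
- Excess: 1 - (1-p)(1-q) - q = p(1-q).

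| p | q | Row as written | Row as remainder | Excess (points) |
|---|---|---|---|---|
| 20% | 20% | 36% | 20% | 16 |
| 20% | 50% | 60% | 50% | 10 |
| 20% | 80% | 84% | 80% | 4 |
| 50% | 20% | 60% | 20% | 40 |
| 50% | 50% | 75% | 50% | 25 |
| 50% | 80% | 90% | 80% | 10 |
| 80% | 20% | 84% | 20% | 64 |
| 80% | 50% | 90% | 50% | 40 |
| 80% | 80% | 96% | 80% | 16 |

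Without independence, the excess is the proportion taking an NSAID and no genuinely other drug. It lies between max(0, p-q) and min(p, 1-q). At p = q = 50% that is from 0 to 50 points, against 25 under independence.

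**3. Where the class is used.** Tables 2.5.1, 3.1 and 3.5.2 test overall concomitant-drug status and MTX (with dose detail), then "status of concomitant drug: corticosteroid, status of concomitant drug: NSAIDs, status of concomitant drug: Other DMARDs". 'Other drugs' is not among their factors. Overall concomitant-drug status does not depend on which class a drug falls in, and the NSAID row is derived from its own rule. Neither changes.

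**The case against.** The strongest reply is that the rule works as written. It is a reproducible definition, and nothing in the SAP says the five layers must be mutually exclusive at drug level. The Table 1.3 note allows redundant counting in this breakdown without limiting it to patients on several drugs. The rows need not sum to 100%, so no total breaks. Table 4.3.4 lists concomitant drugs by name and route, so the class could be rebuilt from the listing. The code list and the analysis-dataset definitions were not available, so whether the omission reached the output cannot be checked.

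Much of this stands. The remainder reading is an inference from the label, from the parallel layers and from the SAP's other 'other' classes; it is not an explicit statement. But the redundancy note does not explain why three of the four named classes are removed and the fourth is kept. A general footnote that patients may be counted more than once would also not tell a reader that 'other drugs' contains NSAIDs.

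A reader might go further and infer that the row carries no information beyond NSAID use. The documents do not support that. The row is the union of NSAID users and users of genuinely other drugs. At p = 20% and q = 80% it would read 84%, against 20% for NSAIDs. The row is mixed, but it does not duplicate the NSAID row. A reader might also infer that the background-factor comparisons are affected; they are not, because this class does not enter them.

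**Conclusion.** The point holds as a definition error with a narrow effect. Followed literally, section 10.1 puts every oral or injected NSAID record in two classes and overstates the 'other drugs' row of Table 1.3, in both analysis sets, relative to what its label suggests. The size cannot be fixed from the documents. The 4 to 64 point range rests on independence and on usage rates of 20% to 80%; the true excess would be near zero if almost all NSAID users also take some genuinely other drug. No single figure should be quoted. This is a minor correction.

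**What to change.** In SAP section 10.1, add NSAIDs (oral + injection) to the classes excluded from the concomitant 'other drugs' definition. Produce that row of Table 1.3 under the corrected rule for both the safety and the efficacy analysis sets. If the overlap is intended, keep the rule and state in a Table 1.3 footnote that 'other drugs' includes NSAIDs.

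The cost is one phrase in the SAP and one table row in two analysis sets, or one footnote. No new data are needed and no other table has to be re-run. When making the change, check how the code list treats NSAIDs that are neither oral nor injected. If it leaves them out of its NSAID category, they stay under 'other drugs' after the correction, and the footnote should say so.
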